Figure (70): Bar chart showing mean of pretreatment, post treatment records and difference between them regarding crown inclination - angular dental measurements in group II.

- **Comparison between both groups:**

Comparison between group I & II regarding difference between pretreatment & posttreatment records of crown inclination - angular dental measurements was performed by using Mann Whitney test which revealed insignificant difference between them regarding all measurements except U6 (Group I was significantly lower than group II) as $P < 0.05$, as presented in table (29) and figure (71).

Table (29): Comparison between both groups regarding crown inclination - angular dental measurements:

Difference Crown Inclination Angular Dental Measurements	Group I		Group II		P value
	MD	SD	MD	SD	
U4	7.14	7.61	7.66	7.31	0.86
U5	7.32	6.86	5.98	8.45	0.71
U6	-0.03	3.87	4.13	3.66	0.04*
U7	2.19	5.81	3.99	5.11	0.27

SD: standard deviation

MD: mean difference

P: probability level which is significant at $P \leq 0.05$

[figure not shown]

Figure (71): Bar chart showing comparison between both groups regarding crown inclination - angular dental measurement.

2. Linear

a. Anteroposterior

- Group I:**

In group I pretreatment records, post treatment records and difference between them regarding anteroposterior- linear- dental measurements were presented in table (30) and figure (72). Comparison between pretreatment & post treatment records was performed by using Paired t-test which revealed insignificant difference between them in all measurements as $P > 0.05$ except U4-apex/S Ver and U5-apex/S Ver (Post was significantly higher than prerecord), MBc6/S Ver (Post was significantly lower than prerecord), as there was a statistical significant difference as $P < 0.05$, while in U5-tip/S Ver (Post was higher than pre), U6-apex/S Ver, MBc7/S Ver and U7-apex/S Ver (post was lower than pre) there was a highly statistical significant difference as $P < 0.0001$, as presented in table (30).

Table (30): Mean & standard deviation of pretreatment, post treatment records and difference between them regarding anteroposterior - linear dental measurements in group I:

Group I Anteroposterior Linear Dental Measurements	Pre		Post		Difference		P value
	M	SD	M	SD	MD	SD	
U1-tip/S Ver	78.77	6.89	78.79	7.17	0.02	0.47	78.77
U1-apex/S Ver	66.06	3.55	66.04	3.69	-0.02	1.21	0.861
L1-tip/S Ver	72.47	3.99	71.31	4.58	-1.16	2.50	0.948
U4-tip/S Ver	61.06	3.77	62.11	3.94	1.06	1.17	0.124
U4-apex/S Ver	57.08	3.56	59.67	3.11	2.59	1.64	0.010*
U5-tip/S Ver	54.68	3.61	56.08	3.71	1.40	1.00	0.000**
U5-apex/S Ver	52.57	2.51	54.42	2.71	1.86	1.55	0.001*
MBc6/S Ver	48.60	3.53	44.82	3.35	-3.78	1.31	0.002*
U6-apex/S Ver	47.70	3.06	44.92	2.83	-2.78	1.64	0.000**
MBc7/S Ver	37.47	3.57	34.21	3.32	-3.26	1.55	0.000**
U7-apex/S Ver	37.79	2.65	35.29	3.44	-2.50	2.45	0.000**
overjet	6.30	3.52	7.48	5.46	1.19	2.43	0.311

M: mean

SD: standard deviation

MD: mean difference

P: probability level which is significant at $P \leq 0.05$

[figure not shown]

Figure (72): Bar chart showing mean of pretreatment, post treatment records and difference between them regarding anteroposterior - linear dental measurements in group I.

- **Group II:**

In group II pretreatment records, post treatment records and difference between them regarding anteroposterior- linear- dental measurements were presented in table (31) and figure (73).

Comparison between pretreatment & post treatment records was performed by using Paired t-test which revealed insignificant difference between them in all measurements as $P > 0.05$ except U4-apex/S Ver U5-tip/S Ver, U5-apex/S Ver (Post was significantly higher than prerecord and MBc6/S Ver , U6-apex/S Ver , MBc7/S Ver & U7-apex/S Ver (Post was significantly lower than prerecord), as there was a statistical significant difference as $P < 0.05$, , as presented in table (31).

Table (31): Mean & standard deviation of pretreatment, post treatment records and difference between them regarding anteroposterior - linear dental measurements in group II:

Group II Anteroposterior Linear Dental Measurements	pre		post		Difference		P value
	M	SD	M	SD	MD	SD	
U1-tip/S Ver	76.89	2.86	77.48	2.99	0.59	0.13	0.12
U1-apex/ S Ver	67.13	3.09	67.56	3.18	0.43	0.08	0.25
L1-tip/S Ver	72.48	3.32	71.93	4.20	-0.54	1.61	0.342
U4-tip/S Ver	63.21	3.81	64.32	4.43	1.11	1.76	0.095
U4-apex/S Ver	57.90	3.53	59.69	2.68	1.79	1.19	0.002*
U5-tip/S Ver	56.43	3.58	58.31	3.87	1.88	1.49	0.005*
U5-apex/S Ver	53.48	2.83	54.85	2.27	1.37	1.58	0.031*
MBc6/S Ver	50.55	3.53	46.04	5.61	-4.51	3.39	0.004*
U6-apex/S Ver	48.06	3.97	45.94	5.17	-2.12	2.52	0.035*
MBc7/S Ver	39.93	3.98	34.61	5.39	-5.32	3.62	0.002*
U7-apex/S Ver	39.18	3.01	36.79	2.75	-2.40	0.98	0.000**
overjet	4.46	1.63	5.31	1.99	0.85	1.25	0.074

M: mean

SD: standard deviation

MD: mean difference

P: probability level which is significant at $P \leq 0.05$

[figure not shown]

Figure (73): Bar chart showing mean of pretreatment, post treatment records and difference between them regarding anteroposterior linear dental measurements in group II.

- **Comparison between both groups:**

Comparison between group I & II regarding difference between pretreatment & posttreatment records of anteroposterior - linear dental measurements was performed by using Mann Whitney test which revealed insignificant difference between them regarding all measurements except U1-tip/S Ver (Group I was significantly lower than group II) as $P <0.05$, as presented in table (32) and figure (74).

Table (32): Comparison between both groups regarding anteroposterior - linear dental measurements:

[figure not shown]
Difference Anteroposterior Linear Dental Measurements	Group I		Group II		P value
	MD	SD	MD	SD	
U1-tip/S Ver	0.02	0.47	0.59	0.13	0.002*
U1-apex/ S Ver	-0.02	1.21	0.43	0.08	0.28
L1-tip/S Ver	-1.16	2.50	-0.54	1.61	1
U4-tip/S Ver	1.06	1.17	1.11	1.76	0.97
U4-apex/S Ver	2.59	1.64	1.79	1.19	0.31
U5-tip/S Ver	1.40	1.00	1.88	1.49	0.71
U5-apex/S Ver	1.86	1.55	1.37	1.58	0.71
MBc6/S Ver	-3.78	1.31	-4.51	3.39	0.8
U6-apex/S Ver	-2.78	1.64	-2.12	2.52	1
MBc7/S Ver	-3.26	1.55	-5.32	3.62	0.12
U7-apex/S Ver	-2.50	2.45	-2.40	0.98	0.86
overjet	1.19	2.43	0.85	1.25	0.75

SD: standard deviation

MD: mean difference

P: probability level which is significant at $P \leq 0.05$

Figure (74): Bar chart showing comparison between both groups regarding anteroposterior linear dental measurements.

b. Vertical

- Group I:**

In group I pretreatment records, post treatment records and difference between them regarding vertical- linear- dental measurements were presented in table (33) and figure (75).

Comparison between pretreatment & post treatment records was performed by using Paired t-test which revealed significant difference between them in all measurements as $P < 0.05$ except overbite as there was insignificant difference between pre & post as $P > 0.05$. In U1-tip/PP, pre was significantly lower than post, while in U4-tip/PP, U5-tip/PP, MBc6/PP, MBc7/PP and L1-tip/PP pre was significantly higher than post as $P < 0.05$, as presented in table (33).

Table (33): Mean & standard deviation of pretreatment, post treatment records and difference between them regarding vertical - linear dental measurements in group I:

Group I Vertical Linear Dental Measurements	Pre		Post		Difference		P value
	M	SD	M	SD	MD	SD	
U1-tip/PP	27.68	3.67	27.86	3.67	0.18	0.52	0.005*
U4-tip/PP	25.79	3.18	25.10	3.00	-0.69	0.56	0.001*
U5-tip/PP	25.25	2.82	24.56	3.01	-0.70	0.63	0.001*
MBc6/PP	23.90	2.50	22.75	2.75	-1.15	0.88	0.003*
MBc7/PP	21.43	2.81	20.77	3.24	-0.65	0.91	0.001*
L1-tip/PP	24.45	3.73	23.63	5.55	-0.82	2.67	0.008*
overbite	3.23	1.14	4.23	2.57	1.00	2.68	0.119

M: mean

SD: standard deviation

MD: mean difference

P: probability level which is significant at $P \leq 0.05$

[figure not shown]

Figure (75): Bar chart showing mean of pretreatment, post treatment records and difference between them regarding vertical linear dental measurements in group I.

- **Group II:**

In group II pretreatment records, post treatment records and difference between them regarding vertical- linear- dental measurements were presented in table (34) and figure (76).

Comparison between pretreatment & post treatment records was performed by using Paired t-test which revealed insignificant difference between them in all measurements as $P > 0.05$ except U4-tip/PP, MBc6/PP & MBc7/PP as Pre was significantly higher than post as $P < 0.05$., as presented in table (34).

Table (34): Mean & standard deviation of pretreatment, post treatment records and difference between them regarding vertical - linear dental measurements in group II:

Group II Vertical Linear Dental Measurements	pre		post		Difference		P value
	M	SD	M	SD	M	SD	
U1-tip/PP	27.78	3.27	28.05	3.19	0.27	-0.09	0.16
U4-tip/PP	25.98	2.93	25.25	3.13	-0.73	0.86	0.036*
U5-tip/PP	25.21	3.05	24.76	3.62	-0.45	1.36	0.352
MBc6/PP	24.00	3.28	22.47	3.13	-1.53	1.21	0.005*
MBc7/PP	22.00	3.65	20.11	3.72	-1.88	1.83	0.015*
L1-tip/PP	24.74	4.08	24.18	4.37	-0.56	1.79	0.374
overbite	3.56	2.61	4.67	2.43	1.11	1.47	0.053

M: mean

SD: standard deviation

MD: mean difference

P: probability level which is significant at $P \leq 0.05$

[figure not shown]

Figure (76): Bar chart showing mean of pretreatment, post treatment records and difference between them regarding vertical linear dental measurements in group II.

- **Comparison between both groups:**

Comparison between group I & II regarding difference between pretreatment & posttreatment records of vertical - linear dental measurements was performed by using Mann Whitney test which revealed insignificant difference between them regarding all measurements, as presented in table (35) and figure (77).

Table (35): Comparison between both groups regarding vertical - linear dental measurements:

Difference Vertical Linear Dental Measurements	Group I		Group II		P value
	MD	SD	MD	SD	
U1-tip/PP	0.18	0.52	0.27	-0.09	0.61
U4-tip/PP	-0.69	0.56	-0.73	0.86	0.81
U5-tip/PP	-0.70	0.63	-0.45	1.36	0.86
MBc6/PP	-1.15	0.88	-1.53	1.21	0.81
MBc7/PP	-0.65	0.91	-1.88	1.83	0.11
L1-tip/PP	-0.82	2.67	-0.56	1.79	0.65
overbite	1.00	2.68	1.11	1.47	0.27

SD: standard deviation

MD: mean difference

P: probability level which is significant at $P \leq 0.05$

[figure not shown]

Figure (77): Bar chart showing comparison between both groups regarding vertical linear dental measurements

c. Transverse

- **Group I:**

In group I pretreatment records, post treatment records and difference between them regarding transverse- linear- dental measurements were presented in table (36) and figure (78).

Comparison between pretreatment & post treatment records was performed by using Paired t-test which revealed significant difference between them in all measurements as $P < 0.05$ except U4 as there was insignificant difference between pre & post as $P > 0.05$. In U5, there was a statistically significant difference as $P < 0.05$ (pre was significantly lower than post), while in U6 and U7 there was a highly statistical significant difference as $P < 0.001$ (pre was significantly lower than post), as presented in table (36).

Table (36): Mean & standard deviation of pretreatment, post treatment records and difference between them regarding transverse - linear dental measurements in group I:

Group I Transverse Linear Dental Measurements	Pre		Post		Difference		P value
	M	SD	M	SD	MD	SD	
U4	16.80	2.01	18.55	2.03	1.75	1.36	0.438
U5	18.83	2.06	20.84	1.94	2.01	1.11	0.001*
U6	21.96	2.21	23.39	2.06	1.43	0.98	0.000**
U7	24.50	2.55	25.45	2.50	0.95	1.01	0.000**

M: mean

SD: standard deviation

MD: mean difference

P: probability level which is significant at $P \leq 0.05$

[figure not shown]

Figure (78): Bar chart showing mean of pretreatment, post treatment records and difference between them regarding transverse - linear dental measurements in group I.

- **Group II:**

In group II pretreatment records, post treatment records and difference between them regarding transverse- linear- dental measurements were presented in table (37) and figure (79).

Comparison between pretreatment & post treatment records was performed by using Paired t-test which revealed insignificant difference between them in all measurements as $P < 0.05$, as presented in table (37).

Table (37): Mean & standard deviation of pretreatment, post treatment records and difference between them regarding transverse - linear dental measurements in group II:

Group II Transverse Linear Dental Measurements	pre		post		Difference		P value
	M	SD	M	SD	M	SD	
U4	17.45	2.12	18.04	2.02	0.60	1.95	0.387
U5	20.04	1.82	20.80	2.00	0.76	1.59	0.188
U6	23.01	1.76	23.66	1.35	0.65	1.15	0.130
U7	25.04	2.14	25.06	1.80	0.02	2.30	0.984

M: mean

SD: standard deviation

MD: mean difference

P: probability level which is significant at $P \leq 0.05$

[figure not shown]

Figure (79): Bar chart showing mean of pretreatment, post treatment records and difference between them regarding transverse - linear dental measurements in group II.

- **Comparison between both groups:**

Comparison between group I & II regarding difference between pretreatment & posttreatment records of transverse – linear dental measurements was performed by using Mann Whitney test which revealed insignificant difference between them regarding all measurements except U5 (Group I was significantly higher than group II) as $P < 0.05$, as presented in table (38) and figure (80).

Table (38): Comparison between both groups regarding transverse - linear dental measurements:

Difference Transverse Linear Dental Measurements	Group I		Group II		P value
	MD	SD	MD	SD	
U4	1.75	1.36	0.60	1.95	0.19
U5	2.01	1.11	0.76	1.59	0.04*
U6	1.43	0.98	0.65	1.15	0.09
U7	0.95	1.01	0.02	2.30	0.31

SD: standard deviation

MD: mean difference

P: probability level which is significant at $P \leq 0.05$

[figure not shown]

Figure (80): Bar chart showing comparison between both groups regarding transverse -linear dental measurements.

C. Soft tissue

- **Group I:**

In group I pretreatment records, post treatment records and difference between them regarding soft tissue measurements were presented in table (39) and figure (81,82).

Comparison between pretreatment & post treatment records was performed by using Paired t-test which revealed insignificant difference between them in all measurements as $P > 0.05$, as presented in table (39).

Table (39): Mean & standard deviation of pretreatment, post treatment records and difference between them regarding soft tissue measurements in group I:

Group I Soft tissue Measurements	Pre		Post		Difference		P value
	M	SD	M	SD	MD	SD	
Ls/E-line distance	2.72	1.27	2.81	0.74	0.10	0.70	0.643
Li/E-line distance	2.40	1.58	2.05	1.46	-0.36	0.96	0.226
NLA angle	97.44	12.44	98.61	13.17	1.17	3.37	0.253

M: mean

SD: standard deviation

MD: mean difference

P: probability level which is significant at $P \leq 0.05$

[figure not shown]

Figure (81): Bar chart showing mean of pretreatment, post treatment records and difference between them regarding Ls/E-line distance & Li/E-line distance in group I.

[figure not shown]

Figure (82): Bar chart showing Mean of pretreatment, post treatment records and difference between them regarding NLA angle in Group I.

- **Group II:**

In group II pretreatment records, post treatment records and difference between them regarding soft tissue measurements were presented in table (40) and figure (83,84).

Comparison between pretreatment & post treatment records was performed by using Paired t-test which revealed insignificant difference between them in all measurements as $P > 0.05$, as presented in table (40).

Table (40): Mean & standard deviation of pretreatment, post treatment records and difference between them regarding soft tissue measurements in group II:

Group II Soft tissue Measurements	Pre		Post		Difference		P value
	M	SD	M	SD	MD	SD	
Ls/E-line distance	3.61	2.78	3.22	2.14	-0.40	2.34	0.625
Li/E-line distance	2.86	2.00	2.23	1.74	-0.63	2.13	0.403
NLA angle	105.30	9.52	105.91	6.47	0.61	3.98	0.656

M: mean SD: standard deviation MD: mean difference

P: probability level which is significant at $P \leq 0.05$

[figure not shown]

Figure (83): Bar chart showing mean of pretreatment, post treatment records and difference between them regarding Ls/E-line distance & Li/E-line distance in group II.

[figure not shown]

Figure (84): Bar chart showing mean of pretreatment, post treatment records and difference between them regarding Mean of NLA angle in Group II.

- **Comparison between both groups:**

Comparison between group I & II regarding difference between pretreatment & posttreatment records of soft tissue measurements was performed by using Mann Whitney test which revealed insignificant difference between them regarding all measurements, as presented in table (41) and figure (85).

Table (41): Comparison between both groups regarding soft tissue measurements:

Difference Soft tissue Measurements	Group I		Group II		P value
	MD	SD	MD	SD	
Ls/E-line distance	0.10	0.70	-0.40	2.34	0.75
Li/E-line distance	-0.36	0.96	-0.63	2.13	0.71
NLA angle	1.17	3.37	0.61	3.98	0.35

SD: standard deviation

MD: mean difference

P: probability level which is significant at $P \leq 0.05$

[figure not shown]

Figure (85): Bar chart showing comparison between both groups regarding soft tissue measurement

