The aim of this study is to evaluate the effect of using coil spring and mini screw anchorage system during maxillary molars distalization.

Study methodology

Study population:

This Randomized Clinical study will be conducted on 20 patients with age ranging from 18 to 25 years, selected from the outpatient clinic of the Orthodontic Department, Faculty of dentistry, Ain Shams University.

The subjects will be selected to fulfill the following inclusion criteria:

1. Skeletal class I, or mild to moderate skeletal class II malocclusion.
2. Full cusp or end to end class II molar relationship.
3. Mild to moderate crowding in the upper dental arch and/or increased overjet.
4. Any other indication requiring maxillary molar distalization unilaterally or bilaterally.
5. Full permanent dentition with exclusion of third molars.
6. Both first and second maxillary molars are in occlusion.
7. Normal or horizontal growth pattern.
8. Non-extraction treatment plan.
9. All subjects are free from any dental anomalies as well as periodontal and systemic diseases that may influence orthodontic treatment.

Exclusion criteria:

1. Previous orthodontic treatment.
2. Severe profile convexity requiring orthognathic surgery.
3. High mandibular angle.
4. Severe molar rotation.
5. Poor oral hygiene.
6. Severe carious lesions.

Study procedure:

An informed consent will be signed by the patients before their enrollment in the current study in which the aim of the study, the methodology and possible complications will be clearly described. This research will be reviewed by research ethics committee, Faculty of dentistry, Ain Shams University.

- Full orthodontic records will be taken for patients who meet the inclusion criteria.
These records are:
 - 1- Extra-oral and intra-oral photographs.
 - 2- Orthodontic study casts.
 - 3- Panoramic radiograph: will be used to detect any dental or bone anomalies, general periodontal condition & bone level, stage of eruption & position of third molars.
 - 4- Lateral cephalometric radiograph: will be used to determine skeletal pattern & mandibular plane angle to verify fitting the inclusion criteria.
- Extra orthodontic records: Cone Beam Computed Tomography.
- The randomization will be through computer generated selection software.

Procedure:

- The maxillary first and second molars will be banded. Brackets will be bonded to the maxillary first and second premolars.

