- Leveling of these segments will be carried out using orthodontic wires sequentially, till 0.019" x 0.025" stainless steel archwire is reached.
- Segmented stiff 0.019" x 0.025" stainless steel archwire will be used to minimize the distal tipping and rotation of the molars. It will be extended from the maxillary second molar to the maxillary first premolar.
- In the first approach, a nickel titanium open coil spring will be inserted mesial to the maxillary first molar to provide distalizing force. In the second approach, two pieces of nickel titanium open coil springs will be inserted mesial to the maxillary first molar and mesial to the maxillary second molar.
- Mini screw anchorage system will be used as a mean of indirect anchorage.
- The patients will be seen every four weeks for reactivation until Class I molar relationship is obtained, as assessed clinically.

Methods of assessment:

- The rate of tooth movement will be analyzed using computer software on digital models obtained every four weeks. When a Class I molar relationship is obtained distalization will be considered achieved, which will be assessed clinically.
- Cone beam computed tomography (CBCT) will be taken for every patient pre-treatment and post-distalization.

Adverse event reporting

Anticipated adverse effects regarding the use of mini screw and its remedy

1. **Pain and discomfort:** If present, it may last 1–2 days and could be reduced by instructing the patient to use warm mouth rinse containing local anesthetic agent.
2. **Irritation to the buccal mucosa:** Bonding resin or a periodontal wound dressing could be applied to the head of the mini screw to smooth its surface and to minimize soft-tissue irritation.
3. **Inflammation around mini screw:** The screws need to be thoroughly cleaned. Mild infections can be controlled by using antiseptic mouthwash and by regular brushing.
4. **Mini screw mobility or failure:** The patient will be instructed to avoid manipulating the screw with fingers, tongue, or with foreign objects like pens. The mini screw could be tightened and left for 1–2 months with no loading, or light loading if necessary. If stability cannot be regained, the mini screw will be removed and replaced.

Statistical analysis

All gathered data will be tabulated and statistically analyzed.

References

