Document Date: June 23, 2022

Three Dimensional Assessment of Maxillary Molars Following Distalization Using Two Different Approaches

A Thesis
Submitted to Faculty of Dentistry
Ain-Shams University
In Partial Fulfillment of the Requirements of
Master's Degree in Orthodontics

Faculty of Dentistry
Ain Shams University
2022

Statistical analysis

Statistical analysis was performed with SPSS 20^{®*}, Graph Pad Prism^{®**}, and Microsoft Excel 2016^{***}.

All quantitative data were explored for normality by using Shapiro Wilk Normality test and presented as means and standard deviation (SD) values. All qualitative data were presented as frequency & percentage. All data were presented in (43) tables & (38) graphs.

Tests used:

- Comparisons 2 different groups was performed by using Mann Whitney test.
- Comparisons 2 successive follow ups periods was performed by using Paired t-test.
- Comparison between quantitative continuous data (Age & Duration) was performed by Independent t-test.
- Comparison between qualitative dichotomous data (Gender) was performed by Chi square test.
- Reliability test was performed by using Intra-class Correlation Coefficient (ICC).

* Statistical Package for Social Science, IBM, Armonk, NY, USA.

** Graph Pad Technologies, San Diego, CA, USA

*** Microsoft Co-operation, Redmond, WA, USA.

* All results presented as:

I. Normality test.

II. Baseline characteristics:

- A. Age.
- B. Gender.
- C. Duration
- D. Pretreatment measurements. (Appendix IV).

III. Measurements

The following measurements were carried for both group I and group II as well as in comparison between the two groups.

A. Skeletal measurements

- 1. Skeletal antero-posterior measurements.
- 2. Skeletal vertical measurements.

B. Dental measurements

- 1. Angular
- 2. Linear

C. Soft tissue measurements.

IV. Reliability: (Appendix V)

- A. Inter-observer.
- B. Intra-observer.

I. Normality test:

Exploration of the given data was performed using Shapiro-Wilk test and Kolmogorov-Smirnov test for normality. As Listed in (Table 11) and showed in (Figure 53), it was revealed that the significant level (P-value) was shown to be insignificant as P-value > 0.05 , which indicated that alternative hypothesis was rejected, and the concluded data originated from normal distribution (parametric data) resembling normal Bell curve in pre & post measurements while P value was significant in the difference between both groups which indicated nonparametric data.

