Comparison between pretreatment & post treatment records was performed by using Paired t-test which revealed insignificant difference between them in all measurements as $P > 0.05$ except U1-FHP and U5-FHP (Post was significantly higher than prerecord) as $P < 0.05$, as presented in table (21).

Table (21): Mean & standard deviation of pretreatment, post treatment records and difference between them regarding anteroposterior angular dental measurements in group I:

Group I Anteroposterior Angular Dental Measurements	Pre		Post		Difference		P value
	M	SD	M	SD	MD	SD	
U1-NA	25.83	9.57	26.27	10.17	0.44	1.88	0.437
U1-FHP	123.54	12.59	124.50	12.88	0.97	1.46	0.042*
U4-FHP	102.14	9.64	103.24	11.70	1.10	4.80	0.444
U5-FHP	96.83	11.01	101.88	13.25	5.06	6.02	0.014*
U6-FHP	94.43	8.90	89.70	9.02	-4.72	9.69	0.119
U7-FHP	87.70	10.16	82.83	8.09	-4.87	8.16	0.063

M: mean

SD: standard deviation

MD: mean difference

P: probability level which is significant at $P \leq 0.05$

[figure not shown]

Figure (63): Bar chart showing mean of pretreatment, post treatment records and difference between them regarding anteroposterior angular dental measurements in group I.

- **Group II:**

In group II pretreatment records, post treatment records and difference between them regarding anteroposterior- angular- dental measurements were presented in table (22) and figure (64).

Comparison between pretreatment & post treatment records was performed by using Paired t-test which revealed insignificant difference between them in all measurements as $P > 0.05$ except U4-FHP and U5-FHP (Post records were significantly higher than prerecords), and U6-FHP (Post record was significantly lower than prerecord) as $P < 0.05$, as presented in table (22).

Table (22): Mean & standard deviation of pretreatment, post treatment records and difference between them regarding anteroposterior angular dental measurements in group II:

Group II Anteroposterior Angular Dental Measurements	pre		post		Difference		P value
	M	SD	M	SD	MD	SD	
U1-NA	16.88	4.94	17.05	5.79	0.18	0.85	0.67
U1-FHP	114.61	4.00	115.05	4.83	0.43	0.83	0.44
U4-FHP	105.26	5.30	109.68	4.81	4.42	5.18	0.034*
U5-FHP	102.27	4.80	108.52	5.79	6.25	5.34	0.008*
U6-FHP	97.77	1.80	84.23	9.21	-13.54	8.61	0.002*
U7-FHP	88.47	8.81	80.17	9.62	-8.30	0.81	0.077

M: mean

SD: standard deviation

MD: mean difference

P: probability level which is significant at $P \leq 0.05$

[figure not shown]

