Figure (64): Bar chart showing pretreatment, post treatment records and difference between them regarding anteroposterior angular dental measurements in group II.

- **Comparison between both groups:**

Comparison between group I & II regarding difference between pretreatment & posttreatment records of anteroposterior angular dental measurements was performed by using Mann Whitney test which revealed insignificant difference between them regarding all measurements except U6-FHP (Group I was significantly higher than group II) as $P < 0.05$, as presented in table (23) and figure (65).

Table (23): Comparison between both groups regarding anteroposterior angular dental measurements:

Difference Anteroposterior Angular Dental Measurements	Group I		Group II		P value
	MD	SD	MD	SD	
U1-NA	0.44	1.88	0.18	0.85	0.70
U1-FHP	0.97	1.46	0.43	0.83	0.33
U4-FHP	1.10	4.80	4.42	5.18	0.82
U5-FHP	5.06	6.02	6.25	5.34	0.61
U6-FHP	-4.72	9.69	-13.54	8.61	0.03*
U7-FHP	-4.87	8.16	-8.30	0.81	0.16

SD: standard deviation

MD: mean difference

P: probability level which is significant at $P \leq 0.05$

[figure not shown]

Figure (65): Bar chart showing comparison between both groups regarding anteroposterior angular dental measurements.

b. Rotation

- **Group I:**

In group I pretreatment records, post treatment records and difference between them regarding rotation- angular- dental measurements were presented in table (24) and figure (66).

Comparison between pretreatment & post treatment records was performed by using Paired t-test which revealed insignificant difference between them in all measurements as $P > 0.05$ except U5-MSP and U7-MSP as there was a statistical significant difference as $P < 0.05$ (Post was significantly higher than prerecord), while in U6-MSP there was a highly statistical significant difference as $P < 0.001$ (Post was significantly higher than prerecord) as presented in table (24).

Table (24): Mean & standard deviation of pretreatment, post treatment records and difference between them regarding rotation angular dental measurements in group I:

Group I Rotation Angular Dental Measurements	Pre			Post			P value
	M	SD	M	SD	MD	SD	
U4-MSP	71.89	6.73	74.95	6.62	3.06	8.70	0.248
U5-MSP	68.84	7.63	63.36	7.23	-5.48	4.79	0.002*
U6-MSP	32.38	6.45	50.50	10.29	18.12	8.35	0.000**
U7-MSP	42.42	9.67	53.25	11.15	10.84	8.06	0.001*

M: mean

SD: standard deviation

MD: mean difference

P: probability level which is significant at $P \leq 0.05$

[figure not shown]

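### Between-group results are bare Mann-Whitney P values on raw change, with no baseline term and no difference with a CI; of the four flagged contrasts that can be checked, only U5-MSP is secure

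*SAP*

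**What the plan says.** The protocol randomises ("The randomization will be through computer generated selection software") but names no analysis method: "All gathered data will be tabulated and statistically analyzed".

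Under Tests used, the SAP says "Comparisons 2 different groups was performed by using Mann Whitney test". The text before each between-group table (Tables 17, 20, 23, 26, 29, 32, 35, 38 and 41) shows that the variable tested is change. For Table 23, for example, the comparison was made "regarding difference between pretreatment & posttreatment records of anteroposterior angular dental measurements was performed by using Mann Whitney test". The reason given for a rank test is the normality check: pre and post values passed, "while P value was significant in the difference between both groups which indicated nonparametric data".

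Pretreatment values appear in the results outline as a baseline item, "Pretreatment measurements. (Appendix IV", and in no between-group model. The between-group tables print each arm's mean change, its SD and a P value.

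Five contrasts are called significant: U6-FHP (P 0.03), U5-MSP (0.009), U6 crown inclination (0.04), U1-tip/S Ver (0.002) and U5 transverse (0.04). The wording for the first is "except U6-FHP (Group I was significantly higher than group II".

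**The concern.** Comparing raw change amounts to fixing the slope of post on pre at 1. Where arms of 12 and 9 patients differ at baseline by chance and the true slope is below 1, the arm that starts higher tends to fall further whatever the appliance did. In four of the five flagged contrasts the baseline gap runs opposite to the difference in change, which is the pattern that would enlarge a change-score contrast.

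These five are the only differences between the two approaches that the SAP reports as significant. All carry the same asterisk, so without an estimate and interval a reader cannot tell a secure contrast from one that barely clears 0.05.

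**Working it through.** **Inputs.** n = 12 and 9 (Table 13). Means and SDs of pre, post and change come from Tables 21, 22, 24, 25, 27, 28, 36 and 37. Tests are taken as two-sided.

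**Can the SAP's figures be reproduced?** Mann-Whitney P values need patient-level ranks, so they cannot be rebuilt. The inputs can be checked with a paired t, mean change / (SD/√n). For U6-FHP, Group I gives 4.72/(9.69/√12) = 1.69, P 0.120 against 0.119 printed. Group II, where the SAP reports "U6-FHP (Post record was significantly lower than prerecord", gives 13.54/(8.61/3) = 4.72, P 0.0015 against 0.002. Seven of the eight arm-level inputs agree. The exception is Group I U5 transverse (0.00006 against 0.001). In Table 36 the rebuilt P values for U4, U5 and U6 (0.0010, 0.00006, 0.0004) match those printed one row lower. That suggests a displaced P column rather than a wrong mean or SD, but it is unconfirmed.

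The fifth contrast, U1-tip/S Ver, is set aside. Its Group II change SD of 0.13 equals 2.99 − 2.86 (post SD minus pre SD). It would give t = 0.59/(0.13/3) = 13.6, which cannot be squared with the printed paired P of 0.12.

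**Baseline gaps (Group II minus Group I).** U6-FHP 97.77 − 94.43 = 3.34 (0.49 pooled SD); U5-MSP 7.42 (0.83); U6 inclination −1.85 (0.57); U5 transverse 1.21 (0.62). P for these gaps runs from 0.08 to 0.28.

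**Unadjusted, U6-FHP.** Difference −13.54 − (−4.72) = −8.82. Pooled variance (11×9.69² + 8×8.61²)/19 = 85.6, so SD 9.25 and SE 9.25×√(1/12 + 1/9) = 4.08. On 19 df the 95% CI is −17.4 to −0.3, P 0.044.

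**Common-slope ANCOVA, U6-FHP.** Within-arm covariance c = (s_pre² + s_post² − s_change²)/2.
- Group I: (79.21 + 81.36 − 93.90)/2 = 33.34; slope 33.34/79.21 = 0.42.
- Group II: (3.24 + 84.82 − 74.13)/2 = 6.97; slope 6.97/3.24 = 2.15.
- Pooled slope b = (11×33.34 + 8×6.97)/(11×79.21 + 8×3.24) = 422.4/897.2 = 0.471.
- Adjusted difference = raw − (b − 1)×gap = −8.82 + 0.529×3.34 = −7.05. SE 3.97 on 18 df, 95% CI −15.4 to 1.3, P 0.093.

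Separate slopes are evaluated at the overall baseline mean on 17 df. Absolute values for all four (degrees, except U5 transverse in mm):

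| Contrast | Unadjusted (95% CI) | Student / Welch P | Common slope (95% CI), P | Separate slopes, P | Slopes I / II (interaction P) |
|---|---|---|---|---|---|
| U6-FHP | 8.8 (0.3 to 17.4) | 0.044 / 0.041 | 7.0 (−1.3 to 15.4), 0.093 | 10.2, 0.061 | 0.42 / 2.15 (0.34) |
| U5 transverse | 1.25 (0.02 to 2.48) | 0.047 / 0.064 | 0.97 (−0.28 to 2.23), 0.121 | 0.95, 0.142 | 0.80 / 0.72 (0.82) |
| U6 inclination | 4.2 (0.7 to 7.7) | 0.022 / 0.022 | 3.2 (−0.2 to 6.5), 0.061 | 4.3, 0.015 | 0.31 / 1.68 (0.07) |
| U5-MSP | 14.3 (6.6 to 22.1) | 0.001 / 0.006 | 10.7 (3.2 to 18.1), 0.007 | 10.7, 0.007 | 0.75 / 0.32 (0.27) |

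**Is the shift itself established?** The shift from change score to ANCOVA is (1 − b)×gap, so testing slope = 1 tests it. P is 0.086 for U6-FHP, 0.146 for U5 transverse, 0.038 for U6 inclination and 0.017 for U5-MSP. The 95% interval for the reduction is −0.3 to 3.8 degrees for U6-FHP and −0.1 to 0.7 mm for U5 transverse; both include zero.

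**Robustness.** Moving every printed value within ±0.005 keeps the common-slope P at 0.092–0.094 (U6-FHP), 0.115–0.126 (U5 transverse), 0.059–0.062 (U6 inclination) and 0.0072–0.0075 (U5-MSP). Using 10 per arm, an even split of the protocol's 20 patients, gives 0.100, 0.142, 0.067 and 0.013 in the same order. Of 48 measures, 8 have a Group II change SD that equals post SD minus pre SD within 0.01, ignoring sign, and were left out. Among the 36 unflagged measures that remain, none has P below 0.05 by Student t on change or by ANCOVA.

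**The case against.** The strongest reply is that a rank comparison of change is valid in a randomised trial and that the SAP gives a reason for it. Both parts stand. Nothing here shows the change scores to be biased. But validity on average does not correct the imbalance that occurred. Non-normal change scores do not rule out ANCOVA either, which needs well-behaved residuals; the SAP itself runs paired t-tests on the same changes.

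A reader might infer from the common-slope column that baseline adjustment cuts four of the five flagged effects by 20 to 26%, and that the missing covariate explains their weakness. The documents do not support that. The shrinkage belongs to the common-slope model. Under separate slopes U6-FHP grows from 8.8 to 10.2 and U6 inclination from 4.16 to 4.33. For U6-FHP, Group I supplies 871 of the 897 units of baseline sum of squares (97%), so the pooled slope is nearly Group I's, while Group II's slope rests on a baseline SD of 1.80 in nine patients. U5 transverse is already at Welch P 0.064 with no adjustment.

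Three further points stand. The four contrasts were examined because they were flagged on change, which favours opposing baseline gaps. Five flags among 48 tests compares with 48×0.05 = 2.4 expected if every null were true, and baseline adjustment does not address that. And the SAP announces 43 tables, whereas the text ends after Table 41 with Appendix IV not shown, so the absence of an interval is established only for the text shown.

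**Conclusion.** The point holds as one of reporting and robustness. Between-group evidence on the measurements consists of P values from raw change, with no baseline term and no estimate with an interval, and the flagged contrasts are not equally secure:

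- U5-MSP stands under both slope models. Its equal-variance P of 0.007 is somewhat optimistic, since residual SDs under the common slope are 4.8 and 9.5; allowing for that gives about 0.011 to 0.020.
- U6-FHP and U5 transverse are borderline before adjustment and above 0.05 after it under both models. They are fragile.
- U6 inclination depends on the slope model.

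It would go too far to call any of these differences false. Direction is kept in all four, and slope = 1 is not rejected for U6-FHP or U5 transverse, so their fragility cannot be laid on the missing covariate. The unadjusted intervals (0.3 to 17.4 degrees; 0.02 to 2.48 mm) already show how little is established.

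These are normal-theory results rebuilt from summaries of changes that the SAP calls non-normal. They assume n = 12 and 9 and correctly printed SDs. Patient-level data must confirm them.

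**What to change.** For each between-group comparison, fit ANCOVA of the post-treatment value on arm plus the same measure's pretreatment value, and report the adjusted difference with its 95% CI. Check the residuals (rather than the marginal normality in Table 11), unequal residual variance and the arm-by-baseline interaction. Where slopes differ, give the separate-slopes estimate at the overall baseline mean. Add a rank-based ANCOVA as sensitivity analysis. Describe the flagged contrasts according to the patient-level adjusted results. Before refitting, check the U1-tip/S Ver change SD and the Table 36 P column against the data.

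The cost is one degree of freedom per comparison and a covariate already collected. It should not be presented as a general gain in precision: over the 40 usable measures the SE falls in 21 and rises in 19 (median ratio 0.99). It rises for MBc6/S Ver (1.06 to 1.13) and MBc7/S Ver (1.16 to 1.25), whose non-significant results do not change.
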